# 2.0 OBJECTIVES AND SCIENTIFIC AIMS

**Primary Objective:** To determine the two-year rates of local-regional progression-free interval

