A retrospective review of 66 patients with gross residual or unresectable non-anaplastic nonmedullary thyroid cancer that underwent EBRT with or without low dose concurrent chemotherapy at Memorial Sloan-Kettering Cancer Center showed that the 3-year locoregional progression-free survival rate was 77.3%, with a 3-year overall survival rate of 54.4%. [51]. The median radiation dose was 6630 cGy (Interguartile range 6000-7000cGy). Concurrent low dose radiation sensitizing chemotherapy was administered to 21 of the 66 patients (31.8%) with a non-significant increase in the 3-year locoregional progression-free survival rate (90.0% versus 73.0%). Despite this improvement in local control, there was no difference in the median overall survival (43.1 versus 37.1 months) likely secondary to the fact that patients treated with concurrent chemotherapy had larger volume of disease and a greater incidence of poorly differentiated histology both of which are known negative prognostic factors. These promising results were in a heterogeneous cohort of patients with multiple poor prognostic risk factors, majority of whom had RAI refractory disease. This is the only published series focused on patients with gross residual or unresectable disease. Grade 3 acute mucositis and dysphagia occurred in 11 (16.7 %) and 13 (19.7 %) patients, respectively. The addition of concurrent chemotherapy only resulted in a 10% increase in acute grade 3 hoarseness (10% versus 0%), with no differences in acute or late toxicities for dermatitis, dysphagia, mucositis, nausea, vomiting, fatigue, or need for a reactive feeding tube. Late adverse toxicity was notable for percutaneous endoscopic gastrostomy tube use in 4 patients (6.1 %), though 2 of these patients had the percutaneous endoscopic gastrostomy tube placed prior to EBRT. There was no difference in the late toxicities between EBRT and CCRT patients including hoarseness and need for a feeding tube. Although patients with metastatic disease fared worse than patients with localized thyroid cancer, loco-regional control was still achieved in a significant number of patients (61.4% versus 88.4%). Thus, EBRT should be considered, even for patients with metastatic disease, because progression in the thyroid bed or neck can cause significant morbidity. Thus our update of the MSKCC experience demonstrated that in patients with unresectable disease or gross residual disease, the 3 year locoregional progression-free interval was 73.0% in patients treated with EBRT alone and 90.0% in patients who underwent concurrent low dose radiation sensitizing chemotherapy with only a slight increase in hoarseness that was self resolving.

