## 9.2.2 Standard treatment planning

Treatment will be directed to the primary tumor and bilateral cervical lymph nodes, if applicable. The target volumes and normal tissue structures will be defined using CT (or MRI) and PET images. Patients will be simulated in the treatment position with individualized Aquaplast immobilization masks. All patients will undergo standard of care positron emission and computed tomography (PET/CT) simulation for treatment planning. If a FDG PET/CT was already performed as part of the pretreatment workup, the investigator can fuse the FDG PET/CT with the CT portion of the radiation simulation as per standard of care guidelines in the department of radiation oncology. Standard uptake value, metabolic tumor volume, and total lesion glycolysis from PET/CT scans will be reported. A CT scan with slices of 3mm thickness or less will be acquired through the target region. A margin of 5-10 cm superior and inferior to the target will be scanned with slices of 5mm thickness or less. All patients will be treated with standard IMRT plans. The volumes of interest will be identified on each axial CT slice. GTV will consist of the gross primary tumor and involved lymph nodes. A high risk subclinical clinical target volume (CTV high risk) as well as a lower risk subclinical volume (CTV low risk) will be defined according to the risk associated with the disease site. A planning target volume (PTV) will also be defined to account for biologic and technical uncertainties. Normal structures of interest including the spinal cord, parotid glands, submandibular glands, oral cavity, and larynx will be outlined in 3 dimensions.

The CT data will be transferred to the 3D treatment planning system. A plan using multiple beams will be tailored to the patient's anatomy and disease distribution. The method of inverse-planning will be utilized to determine the intensity profiles of the treatment beams. All dose constraints, maximum, mean, and minimum are standard as per our MSKCC treatment planning guidelines for patients undergoing IMRT for their thyroid cancer.

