# 12.0 CRITERIA FOR THERAPEUTIC RESPONSE/OUTCOME ASSESSMENT

The primary endpoint of this study is to assess the 2-year loco-regional progression-free interval using standard post-radiation imaging studies. Scans will be performed at 3 months (+/- 4 weeks) and 6 months (+/- 4 weeks) post-RT and then every 6 months (+/- 6 weeks) until 2 years post-RT. Patients will be followed for life with standard screening for disease recurrence, according to the schedule in Sections 9 and 10.Patients will be classified as loco-regional progression free as long as there is no evidence of loco-regional progression of disease. Loco-regional failure will be defined as infield progression if included in the RT field and meets one of the following criteria: 25% increase in tumor volume, new lesions, and/or 25% increase in metabolic tumor volume or total lesion glycolysis.

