## **14.0 BIOSTATISTICS**

The primary objective of this study is to determine the 2-year loco-regional progression-free rate. Current literature showed that the 2-year loco-regional progression-free rate is about 40% [16-24]. We expect to improve this rate substantially to 90% by applying the proposed chemoradiation treatment strategy. It should be mentioned that according to previous versions of the protocol 8 patients had been treated with IMRT alone. But prospectively we will treat patients with the current standard which is chemoradiation. To this end we will still employ a single-stage binomial design. We will recruit 19 patients, and we will claim the proposed treatment promising when at least 14 patients are without progression of disease at 2 years from the end of the treatment. This decision rule gives a power (that is, probability of declaring success when the true 2-year progression rate is 90% or higher) of 0.99 with the

type 1 error rate (that is, probability of declaring success when the true 2-year progression rate is 40% or lower) less than 0.01. Patients who died due to any reason, or were lost to F/U within 2 years will be regarded as having loco-regional progression. Patients who do not complete treatment due to excessive toxicity will be excluded from the primary endpoint analysis and replaced by new eligible patients. We expect to accrue the total of 19 analyzable patients in 2 years. The 8 patients who had received IMRT alone will not be counted towards this endpoint and will be summarized separately.

To better understand the loco-regional progression we will also use the cumulative incidence function for summaring the endpoint of time to loco-regional failure, which will be carried out by a competing risks anlaysis. Overall survival rates will be assessed by Kaplan-Meier method. Rates of (acute or late) toxicities will be computed by sample proportions and confidence intervals will also be provided. Summary statistics and/or longitudinal plots for the Modified Barium Swallow-Imp and Penetration-Aspiration scales will be supplied for assessing objective measures of late dysphagia. BRAF and other mutation measurements at baseline will be correlated with clinical outcomes such as overall survival and local-regional control using survival analysis tools. All secondary endpoints will be analyzed for the 19 patients under chemoradiation. The 8 patients who had received IMRT alone will be summarized separately.

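### Section 12 limits loco-regional failure to in-field progression, while the objective, endpoint and design rates are loco-regional with no field limit; applied as written, this can only favour success

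*Combined protocol and SAP*

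**What the plan says.** The primary objective in Section 2.0 is "To determine the two-year rates of local-regional progression-free interval". Sections 1.0 and 4.2 give the endpoint in equivalent terms, and Section 14.0 opens with "The primary objective of this study is to determine the 2-year loco-regional progression-free rate", then sets a 40% literature rate against an expected 90%. None of these mentions the radiation field.

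Section 12.0 has two consecutive sentences on classification. The first is general: "Patients will be classified as loco-regional progression free as long as there is no evidence of loco-regional progression of disease". The second is the working definition: "Loco-regional failure will be defined as infield progression if included in the RT field and meets one of the following criteria". The criteria that follow are a 25% increase in tumour volume, new lesions, or a 25% increase in metabolic tumour volume or total lesion glycolysis. All of them sit under the in-field condition, new lesions included.

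Section 9.2.2 describes the target: "Treatment will be directed to the primary tumor and bilateral cervical lymph nodes, if applicable".

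The decision rule in Section 14.0 calls the treatment promising when "at least 14 patients are without progression of disease at 2 years from the end of the treatment", out of 19. The same section counts death from any cause and loss to follow-up within 2 years as loco-regional progression. It also plans a competing-risks cumulative incidence analysis of time to loco-regional failure.

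**The concern.** The endpoint is named for a region but scored by a treatment field. The reason given in Section 3.0 for caring about it is regional: "progression in the thyroid bed or neck can cause significant morbidity". That harm does not depend on where the field edge lay. Because nodal treatment varies between patients, so does the area in which a failure can be scored.

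Two broader phrases do not settle the matter. The general sentence in Section 12.0 does not say what loco-regional progression is. The phrase in the Section 14.0 rule does not define progression either and, read literally, would also count distant progression. That leaves three possible scopes for one primary event: in-field, loco-regional, or any site.

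At stake is a go/no-go count in 19 patients, where one patient is 1/19 = 5.3 percentage points and one reclassified patient can turn 13 (68.4%) into 14 (73.7%). An in-field event would also understate the cumulative incidence of loco-regional failure.

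**Working it through.** **1. Reproduce the plan's figures.** Inputs from Section 14.0: n = 19, success if X ≥ 14, null rate 0.40, target rate 0.90. The formula is P(X ≥ 14) = Σ C(19,k) p^k (1−p)^(19−k), summed over k = 14 to 19.

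- p = 0.40: 0.0031 (plan: less than 0.01).
- p = 0.90: 0.9914 (plan: 0.99).

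Both reproduce. The sample-size arithmetic is sound; the question is which event the rates refer to.

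**2. Direction.** In-field failures are a subset of loco-regional failures. The success count under the in-field definition is therefore at least the count under the regional definition. Deaths and losses within 2 years are failures under either. The only patients who change class are those alive and followed at 2 years whose only failure was in the neck outside the field.

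**3. Size by count.** With k such patients among 19, the rule acts as a cut-off of 14 − k regional successes. At p = 0.40:

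- k = 1: P(X ≥ 13) = 0.0116.
- k = 2: P(X ≥ 12) = 0.0352.

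**4. Size by rate.** Let q be the proportion of all patients in that group. The documents do not give q, so a range is shown. Assume that the 40% benchmark counts all loco-regional failures. The scored null rate is then 0.40 + q.

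| q | scored rate | P(X ≥ 14) |
|---|---|---|
| 0 | 0.40 | 0.0031 |
| 0.02 | 0.42 | 0.0052 |
| 0.05 | 0.45 | 0.0109 |
| 0.10 | 0.50 | 0.0318 |

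Solving P(X ≥ 14) = 0.01 gives p = 0.4462, so the stated bound is crossed at q = 0.4462 − 0.40 = 0.046. As a share of null failures that is 4.62/60 = 7.7%.

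**5. What widening the definition does to power.** If the 90% target already means all loco-regional failures, power stays at 0.9914. If 90% is an in-field rate, the regional rate is 0.90 − q:

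- q = 0.05: P(X ≥ 14) at p = 0.85 is 0.946.
- q = 0.10: P(X ≥ 14) at p = 0.80 is 0.837.

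**The case against.** The strongest reply is that the plan does not clearly adopt the narrow rule. The sentence just before the definition has no field limit, the Section 14.0 rule is broader still, and the definition itself is awkwardly phrased. A reader might infer that the plan will certainly score every out-of-field neck recurrence as progression-free. The documents do not support that certainty. They do show that the only sentence giving criteria is the narrow one, and that nothing says an out-of-field neck recurrence is a failure.

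Second, field and region may nearly coincide. Section 9.2.2 includes involved nodes in the gross tumour volume and adds high-risk and lower-risk subclinical volumes. Patients with metastatic disease are eligible, so a field limit may have been meant to separate treated from distant disease. This stands as a reason why the effect could be small or nil, and why in-field control could be a legitimate endpoint if it were named as one.

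Third, the one-way direction belongs to the in-field restriction alone. Read literally, the Section 14.0 phrase would count distant progression and lower the success count. That is correct, so the two wording problems together have no single direction.

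A reader might also infer that Sections 12 and 14 conflict over deaths. They do not: Section 14.0 states the rule and Section 12.0 is silent.

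**Conclusion.** The point holds as a mismatch between the stated endpoint and its only working definition, and it should be corrected before outcomes are scored. Applied as written, the definition can only help the treatment reach 14 of 19 or make no difference, relative to counting all loco-regional failures.

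The size is unknown and may be zero. The crossing of 0.01 at about 4.6% of patients, and the values of 0.011 at 5% and 0.032 at 10%, depend on two assumptions: that the 40% benchmark counts all loco-regional failures, which cannot be checked from the documents, and that the affected patients are alive and followed at 2 years with out-of-field failure only. A reader might infer from these figures that the stated type 1 error is wrong. It is not: it reproduces when the rates and the scored event share one definition.

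**What to change.** In Section 12.0, define loco-regional failure as progression or a new lesion in the thyroid bed or regional neck nodes, regardless of the radiation field, and report in-field and out-of-field failures descriptively. Alternatively, if in-field control is what is wanted, name the objective, endpoint and benchmark that way in Sections 2, 12 and 14.

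Under the regional definition, specify freedom from loco-regional progression in the Section 14.0 decision rule. Keep the existing rule on death and loss to follow-up for the binary endpoint. Use one event definition for the binary endpoint, the cumulative incidence analysis and the separate summary of the 8 patients treated with IMRT alone.

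The cost is a wording amendment using imaging already scheduled, although neck CT or MRI is only recommended alongside the FDG PET/CT. N = 19 and the cut-off of 14 do not change. With the regional definition the reported rate may be slightly lower. The amendment should state which definition the 40% and 90% rates refer to, since power is preserved only if the 90% target is regional.

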## **14.0 BIOSTATISTICS**

The primary objective of this study is to determine the 2-year loco-regional progression-free rate. Current literature showed that the 2-year loco-regional progression-free rate is about 40% [16-24]. We expect to improve this rate substantially to 90% by applying the proposed chemoradiation treatment strategy. It should be mentioned that according to previous versions of the protocol 8 patients had been treated with IMRT alone. But prospectively we will treat patients with the current standard which is chemoradiation. To this end we will still employ a single-stage binomial design. We will recruit 19 patients, and we will claim the proposed treatment promising when at least 14 patients are without progression of disease at 2 years from the end of the treatment. This decision rule gives a power (that is, probability of declaring success when the true 2-year progression rate is 90% or higher) of 0.99 with the

type 1 error rate (that is, probability of declaring success when the true 2-year progression rate is 40% or lower) less than 0.01. Patients who died due to any reason, or were lost to F/U within 2 years will be regarded as having loco-regional progression. Patients who do not complete treatment due to excessive toxicity will be excluded from the primary endpoint analysis and replaced by new eligible patients. We expect to accrue the total of 19 analyzable patients in 2 years. The 8 patients who had received IMRT alone will not be counted towards this endpoint and will be summarized separately.

To better understand the loco-regional progression we will also use the cumulative incidence function for summaring the endpoint of time to loco-regional failure, which will be carried out by a competing risks anlaysis. Overall survival rates will be assessed by Kaplan-Meier method. Rates of (acute or late) toxicities will be computed by sample proportions and confidence intervals will also be provided. Summary statistics and/or longitudinal plots for the Modified Barium Swallow-Imp and Penetration-Aspiration scales will be supplied for assessing objective measures of late dysphagia. BRAF and other mutation measurements at baseline will be correlated with clinical outcomes such as overall survival and local-regional control using survival analysis tools. All secondary endpoints will be analyzed for the 19 patients under chemoradiation. The 8 patients who had received IMRT alone will be summarized separately.

Multiparametric and DW scans will also be obtained. Due to the small pilot size of this exploratory aim, we may not produce significant results. In that case, we will present summary statistics and suggest directions for future study.

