
The American Thyroid Association Task Force recommends EBRT for gross residual disease not amenable to surgery or RAI treatment.[25] However, in all patients, the potential benefit of EBRT should be weighed against the acute and long-term risks. Non-randomized studies have identified a potential role for adjuvant treatment of high-risk patients with external beam radiation therapy,[20, 26] documenting improved local control,[18, 21, 23, 27-30] with no survival benefit.[30] The inclusion criteria for receiving external beam radiation therapy have included advanced age (>40 years), extrathyroidal extension, high EORTC score or other scoring system for prognostic variables. Local recurrence has purportedly declined from 20-

25% to 4-7% with the addition of external beam radiation therapy in these studies. This translates to a 65-85% decrease in local recurrence. Of note, these are patients who present with gross residual disease where a second surgery is unlikely.

Given that the data to date are largely retrospective and hypothesis generating, that these retrospective studies reported a heterogenous group of non-anaplastic thyroid cancer patients who underwent EBRT, i.e., both resectable with positive margin to an unresectable cohort, a prospective study is needed to settle the controversies associated with the role of

EBRT in thyroid cancer management. Furthermore, we would like to gather both the acute and late complications associated with EBRT in a prospective manner. In order to minimize heterogeneity, we chose to focus on patients who we believe benefit the most from EBRT, i.e., those with unresectable or gross residual disease.

Although mutations such as BRAF are present in greater than 70% of all papillary thyroid cancers and are known to be associated with a poorer prognosis with increased risk of insensitivity to RAI [31-33], to our knowledge, there is no data on what effects external beam radiation has on tumors with these mutations. Hence, one of the goals of this protocol is to collect tissue in a prospective manner and perform exploratory analyses pre-radiation (at baseline) so that we may further understand this disease and these mutations.

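### The 40% null and 90% target in Section 14.0 are not reconciled with the centre's own series or put on the trial's scoring scale, so the stated error and power are not assured for a comparison with EBRT alone

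*Combined protocol and SAP*

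**What the plan says.** Section 14.0 (Biostatistics) takes its null from the literature: "Current literature showed that the 2-year loco-regional progression-free rate is about 40% [16-24". The target follows: "We expect to improve this rate substantially to 90% by applying the proposed chemoradiation treatment strategy". The rule is a single-stage binomial test: "We will recruit 19 patients, and we will claim the proposed treatment promising when at least 14 patients are without progression of disease". Stated power is 0.99 at 90% and stated type 1 error is below 0.01 at 40%. The same section scores death from any cause, and loss to follow-up, within 2 years as loco-regional progression.

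Section 3.0 (Background and Rationale) describes the centre's retrospective series of 66 patients with gross residual or unresectable non-anaplastic, non-medullary disease, which is the trial population. There, "the 3 year locoregional progression-free interval was 73.0% in patients treated with EBRT alone", against 90.0% with concurrent low-dose chemotherapy. The difference was not significant. The whole-series 3-year figures were 77.3% for loco-regional control and 54.4% for overall survival. The protocol says of this series: "This is the only published series focused on patients with gross residual or unresectable disease". Of the retrospective EBRT literature generally it says that "these retrospective studies reported a heterogenous group of non-anaplastic thyroid cancer patients who underwent EBRT", ranging from resectable disease with positive margins to unresectable disease.

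Section 14.0 does not mention the 73.0%, and does not say why 40% is the better benchmark.

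**The concern.** In a single-arm trial the historical rate carries the whole inference. The 90% target coincides with the chemotherapy result of the centre's series. The null comes from a different and more mixed body of work, and the EBRT-alone result of that same series is left out. The trial has also moved from IMRT alone (8 earlier patients, summarised separately) to chemoradiation, so readers will naturally take a positive result as evidence that chemoradiation improves on radiotherapy alone.

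Two things are at stake. If the EBRT-alone rate on the trial's endpoint is above 40%, the error against that comparator is larger than the one stated. If 90% comes from an endpoint that does not count deaths, the stated power describes a rate that the trial's endpoint may not be able to reach.

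**Working it through.** **Step 1: reproduce the plan.** X is binomial with n = 19, and success is X ≥ 14.
- P(X ≥ 14) at 0.40 = 0.0031, consistent with the stated error below 0.01.
- P(X ≥ 14) at 0.90 = 0.991, matching the stated 0.99.

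The arithmetic in Section 14.0 is right. The question is whether 0.40 and 0.90 are the right inputs.

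**Step 2: is the series on the trial's scale?** If deaths counted as failures, the progression-free rate could not exceed overall survival. In the series it does, 77.3% against 54.4% at 3 years. So the series did not score deaths as failures, even though Section 3.0 calls its measure both an interval and a survival rate. The trial does score them. Neither 73.0% nor 90.0% is therefore a value of the trial's endpoint.

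**Step 3: approximate conversion.** Inputs from Section 3.0: 0.730, 0.900, and overall survival 0.544 (whole series), all at 3 years. Assumptions, not in the documents: constant hazards, and independence of death and loco-regional progression. A 3-year rate S then becomes S^(2/3) at 2 years.
- EBRT alone, loco-regional: 0.730^(2/3) = 0.811
- Chemotherapy, loco-regional: 0.900^(2/3) = 0.932
- Overall survival: 0.544^(2/3) = 0.666
- EBRT alone, trial scoring: 0.811 × 0.666 = 0.540
- Chemotherapy, trial scoring: 0.932 × 0.666 = 0.621

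**Step 4: losses.** The documents give no loss rate. I assume 10% and 20%: 0.540 × 0.9 = 0.486 and 0.540 × 0.8 = 0.432.

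**Step 5: the rule at these rates.**

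| Scenario | Scored rate | P(at least 14 of 19) |
|---|---|---|
| Plan's null | 0.40 | 0.003 |
| EBRT alone, 20% loss | 0.43 | 0.007 |
| EBRT alone, 10% loss | 0.49 | 0.02 |
| EBRT alone, no loss | 0.54 | 0.07 |
| Chemotherapy, no loss | 0.62 | 0.21 |
| Plan's target | 0.90 | 0.991 |

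The error passes 0.01 at a scored rate just below 0.45 (at 0.45 it is 0.011).

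**Step 6: sensitivity to the survival input.** Section 3.0 also gives median survival of 43.1 versus 37.1 months, which I read as chemotherapy first. Constant-hazard 2-year survival is then 0.5^(24/37.1) = 0.639 and 0.5^(24/43.1) = 0.680. The scored rates become 0.811 × 0.639 = 0.518 and 0.932 × 0.680 = 0.634, with P(at least 14 of 19) = 0.04 and 0.25. The picture is unchanged.

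**Step 7: the 90% target.** A rate that counts deaths as failures cannot exceed overall survival. Reaching 0.90 needs 2-year survival of at least 0.90, whereas the series implies about 0.67 under the constant-hazard assumption.

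**The case against.** The protocol promises no test against EBRT alone. It calls treatment promising relative to a literature rate, and it presents itself as a standard-of-care protocol meant partly to collect toxicity prospectively. The series is a weak benchmark: it is retrospective, the EBRT-alone group is about 66 − 21 = 45 patients, and the median dose was 6630 cGy against the 70 Gy planned here. The chemotherapy difference was not significant, in patients with worse prognostic features. Whether 40% fairly summarises references 16-24 cannot be checked from these documents. With enough loss to follow-up, the EBRT-alone rate on the trial's scoring falls below 0.45 and the stated error holds.

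All of this stands, and it limits the size of the point. It does not explain why one arm of the series matches the target while the other arm is absent from the null, nor why the target is stated on a scale that ignores deaths.

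A reader might go further: put 73.0% straight into the rule, notice that the cut-off 14/19 = 73.7% is almost the same number, and conclude that treatment no better than EBRT alone would pass more often than not. The documents do not support this. By Step 2, the 73.0% ignores deaths that the trial scores as failures, so the resemblance to the cut-off is a coincidence of two different endpoints. For the same reason, a new cut-off should not be derived from 73.0% against 90.0%.

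**Conclusion.** The point holds in a limited form and should be fixed; it does not invalidate the design. The stated operating characteristics are correct for 40% and 90%, but Section 14.0 does not show that these are the right rates on the trial's own endpoint. Against EBRT alone, the chance of a promising result is about 0.007 to 0.07, for scored rates of 0.43 to 0.54. An error below 0.01 is therefore possible but not assured. If chemoradiation performs as in the centre's series, the chance of success is nearer 0.21 than 0.99 before any losses.

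These figures rest on constant hazards, independence of death and progression, whole-series survival applied to both groups, and assumed loss rates of 0 to 20%. Positive dependence between death and progression would raise the scored rates. The small size of the EBRT-alone group adds uncertainty in both directions. It does not follow that the error exceeds 0.01 on every reading.

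**What to change.** In Section 14.0:
- Re-tabulate the institution's series at 2 years from the end of treatment, separately for the EBRT-alone and chemotherapy groups, scoring deaths and losses as failures exactly as the trial does.
- Use the results to justify or replace both 40% and 90%, and state which endpoint definition the 40% from references 16-24 uses.
- Restate the type 1 error and power of the chosen cut-off at n = 19.
- If 14 of 19 is kept, give its error against the re-tabulated EBRT-alone rate. Limit the conclusion to exceeding a 40% historical rate, with no claim of improvement over EBRT alone.

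The cost is one re-tabulation of data the institution should already hold, plus revised wording. Restating and narrowing the claim needs no extra patients. The stated error and power will probably look less favourable. If the converted rates are near 0.54 and 0.62, 14 of 19 separates them poorly (0.07 against 0.21), so a claim over EBRT alone would need a different design, not a change of wording.

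### The 14-of-19 rule counts deaths and losses to follow-up as progression, but its 0.99 power assumes a 90% rate with no survival or loss assumption behind it, and Section 12 defines the outcome without deaths

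*Combined protocol and SAP*

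**What the plan says.** Section 2.0 gives the primary objective as "To determine the two-year rates of local-regional progression-free interval". Section 12.0 has patients "classified as loco-regional progression free as long as there is no evidence of loco-regional progression of disease", and defines failure by in-field criteria only: tumor volume, new lesions, metabolic tumor volume or total lesion glycolysis. It mentions neither death nor loss to follow-up.

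Section 14.0 sets a single-stage binomial rule: 19 patients, with success claimed if at least 14 are without progression 2 years after the end of treatment. The null is a 2-year loco-regional progression-free rate of about 40%, attributed to the literature. For the target it says: "We expect to improve this rate substantially to 90% by applying the proposed chemoradiation treatment strategy". Power is given as the "probability of declaring success when the true 2-year progression rate is 90% or higher) of 0.99" (the printed word should be progression-free), with type I error below 0.01. It then adds: "Patients who died due to any reason, or were lost to F/U within 2 years will be regarded as having loco-regional progression".

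Section 14.0 also plans a competing-risks cumulative incidence analysis of loco-regional failure and a Kaplan-Meier analysis of overall survival.

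**The concern.** A patient who dies at 18 months with a controlled neck is progression-free under Section 12 and a failure under the 14-of-19 rule. The 40% and 90% are described as loco-regional rates, while the rule is applied to a composite of progression, death and loss.

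Section 3.0 contains the only figure in the protocol that supports 90%: "the 3 year locoregional progression-free interval was 73.0% in patients treated with EBRT alone and 90.0% in patients who underwent concurrent" chemotherapy. Section 14 does not name it as the source. In the same series the pooled loco-regional "progression-free survival rate was 77.3%, with a 3-year overall survival rate of 54.4"%. A rate that counted every death as a failure could not exceed overall survival, so that series did not count all deaths. Section 6.2 admits patients with metastatic disease, so deaths without loco-regional progression are to be expected here too.

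The formal claim that the treatment is promising rests on 14 of 19 alone. If deaths or losses cause the rule to fail, the result could be read as poor loco-regional control.

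**Working it through.** **Inputs.** From Section 14: n = 19, success at 14 or more, null 0.40, target 0.90. From Section 3: 3-year loco-regional rates of 90.0% (concurrent chemotherapy, 21 of 66 patients) and 73.0% (EBRT alone); pooled 3-year overall survival of 54.4%; median overall survival of 43.1 and 37.1 months.

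**The plan's own figures.** With X ~ Binomial(19, p):
- P(X ≥ 14) at p = 0.40 is 0.0031 (stated: below 0.01).
- P(X ≥ 14) at p = 0.90 is 0.9914 (stated: 0.99).

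Both reproduce.

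**The success rate under the Section 14 rule.** Here p is the probability of being alive, followed and loco-regionally progression-free at 2 years. If these are independent, p = S × C × (1 − L), where S is 2-year survival, C is 2-year loco-regional control and L is the loss rate. Under any dependence, p cannot exceed S.

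**Two-year values (assumptions).** The documents give none, so they are extrapolated:
- C = 0.90^(2/3) = 0.932, constant hazard.
- S = 0.544^(2/3) = 0.666, constant hazard.
- S = 0.5^(24/43.1) = 0.680, exponential from the 43.1-month median. The 37.1-month median gives 0.639.

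The remaining rows of the table use assumed values of S.

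| S | p = 0.932 × S | P(pass), no losses | P(pass), 5% loss | P(pass), C = 0.90, no losses | Upper limit (p = S) |
|---|---|---|---|---|---|
| 0.666 | 0.621 | 0.21 | 0.14 | 0.16 | 0.35 |
| 0.680 | 0.634 | 0.25 | 0.17 | 0.19 | 0.40 |
| 0.75 | 0.699 | 0.47 | 0.34 | 0.38 | 0.67 |
| 0.80 | 0.746 | 0.65 | 0.51 | 0.55 | 0.84 |
| 0.85 | 0.792 | 0.81 | 0.68 | 0.72 | 0.95 |
| 0.90 | 0.839 | 0.93 | 0.83 | 0.86 | 0.99 |

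The 5% loss column uses C = 0.932 and multiplies p by 0.95.

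**Survival needed.** A pass probability of 0.80, 0.90 or 0.99 needs p = 0.788, 0.825 or 0.897. Dividing by 0.932 gives S = 0.845, 0.885 or 0.962. Even with perfect control and no losses, 0.99 needs S of about 0.90.

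**If deaths and losses were not failures.** On the purely loco-regional scale, the EBRT-alone figure of 73.0% at 3 years gives 0.73^(2/3) = 0.811 at 2 years under constant hazard. The rule would be passed with probability 0.59 at p = 0.73 and 0.87 at p = 0.811.

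**Precision at the boundary.** The exact (Clopper-Pearson) 95% interval for 14/19 is 48.8% to 90.9%.

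**The case against.** Counting deaths and losses as failures is legitimate. A fixed-time binomial endpoint needs a rule for patients whose 2-year status is not observed, and this one is explicit and prespecified. It is also conservative: if the 40% null excludes deaths, the true type I error is below 0.0031. The power is stated conditionally, and the 90% could be read as already including deaths and losses. The rule has slack, keeping power of 0.90 at a composite rate of 0.825. Trial patients may live longer than the retrospective series: they need KPS of at least 70%, and only 21 of those 66 patients had chemotherapy. Section 14 also replaces patients who stop for excessive toxicity and counts 2 years from the end of treatment. The planned competing-risks and survival analyses would help explain a failed rule. Finally, the plan claims only that the treatment is promising, not that it beats IMRT alone.

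Much of this stands. The handling rule need not be dropped, and the size of the power loss is uncertain. But conservatism protects the type I error and does nothing for the power. If the 90% is a composite, the plan does not say so, and it would imply survival well above the institution's own series. More favorable survival helps only in part: at 0.85 the pass probability is 0.81. Taking control as 0.90 instead of 0.93 lowers every figure. The secondary analyses aid interpretation but do not enter the success claim.

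**Conclusion.** The concern holds. The 0.99 is correct binomial arithmetic at p = 0.90, but the plan gives no basis for 90% on the composite that Section 14 analyzes, and Section 12 describes a different outcome. With control of 0.93 independent of death and no losses, the pass probability runs from 0.21 to 0.93 as 2-year survival goes from 0.67 to 0.90. The limits under any dependence are 0.35 to 0.99. The exact size rests on assumed survival, on constant-hazard extrapolation from 3 years and on a 21-patient subgroup. The direction does not, because success cannot exceed survival. The 40% null is not shown to be wrong, but the plan does not say whether it counts deaths and does not reconcile it with the Section 3 series. This should be fixed; the design itself remains usable.

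**What to change.** 1. Use one endpoint definition in Sections 12 and 14 for the null, the target and the 14-of-19 rule. Section 13 treats removal for toxicity as treatment failure and includes all enrolled patients by intent to treat, whereas Section 14 excludes and replaces such patients; these passages need reconciling at the same time.
2. If deaths and losses count as failures, state the assumed 2-year survival and loss rate, with their basis, and replace the single 0.99 with power over a range of survival, as in the table above. If they do not count, state the null and target on that scale and reconcile the null with the 73.0% EBRT-alone figure. On that scale only, the pass probabilities of 0.59 to 0.87 mean that success would not show benefit over IMRT alone.
3. Report the 2-year rate with its exact 95% interval beside the cumulative incidence already planned. State that a rule failed through deaths or losses without loco-regional progression is not evidence of poor loco-regional control.

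The cost is wording in these sections and one small table, with no added patients or visits. The price is a less favorable stated power and a narrower claim.
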